5.1.8 Treatment compliance and accountability

The investigational product should only be used as directed in this protocol. Details of treatment with investigational product for each patient will be recorded in the CRF.

All patients will be requested to complete a dosing diary, including the date and time that each dose is taken. If a dose is missed, the reason must be noted in the diary. A copy of the dosing diary is provided in the study reference material.

Patients should return all unused medication and empty containers to the investigator. The study personnel at the investigational site will account for all drugs dispensed and returned. Unless otherwise authorized by Sponsor, all investigational product supplies unallocated or unused by the patients must be destroyed by procedures approved by Sponsor or returned to Sponsor or its designee. Certificates of delivery and destruction should be signed.

5.2 Benefit/risk and ethical assessment

5.2.1 Potential benefit

EGFR Exon20ins and HER2 Exon20ins occurred in about 4% patients with NSCLC. The prognosis of these patients is poor as there lacks effective treatment. Chemotherapy is the standard of care, but median PFS and OS were only around 6 months and 24 months, respectively.

In preclinical setting, DZD9008 shows *in vitro* activity in cells expressing EGFR sensitizing mutations, T790M mutation, Exon20ins and uncommon mutations as well as HER2 Exon20ins, with weak activity in cells carrying wild type EGFR. *In vivo*, DZD9008 demonstrates promising anti-tumor efficacy in xenograft models carrying EGFR aberrations.

In the two ongoing phase 1 studies of DZD9008 in NSCLC patients with EGFR and HER2 mutations (by April 3, 2023), DZD9008 demonstrated promising anti-tumor efficacy in patients with EGFR Exon20ins with confirmed ORR of and selected dose level of 200 mg and 300 mg, separately. In the phase 2, pivotal study DZ2020E0001 in Chinese NSCLC with EGFR Exon20ins, the confirmed ORR at 300 mg QD was as assessed by IRC. Anti-tumor activity of DZD9008 was also observed in patients with EGFR sensitizing mutation, T790M, as well as in patients with HER2 Exon20ins. DZD9008 was well tolerated up to 400 mg once daily. The incidences of TEAEs at grade 3 and above, TEAEs leading to dose interruption or reduction were lower than the other EGFR TKIs. The types of TEAEs reported were considered to be related to inhibition of wild type EGFR, and majority of TEAEs were mild or moderate, and could be managed or recover.

These data suggest that DZD9008 has a potential to bring clinical benefit to patients with different types of EGFR or HER2 aberrations, especially in patients with EGFR Exon20ins.

Date: July 24,2023

5.2.2 Potential risks identified non-clinically with DZD9008

Section 2.3.4 of this protocol summarizes potential risks based upon non-clinical toxicity studies with DZD9008 in rats and dogs, and in vitro experiments, with further detailed information available in the IB. The monitoring and management of the potential risks based on preclinical findings and clinical EGFR TKIs class effect are discussed below:

5.2.2.1 Gastrointestinal tract effects

Patients with refractory nausea, vomiting and chronic gastrointestinal diseases are excluded from participating in this study. Detailed information on the treatment of gastrointestinal adverse events will be included in the "Guidance for the management of Adverse Events in Studies of DZD9008", which will be provided to the investigators. This guidance is for information sharing only, and investigator can manage these AEs according to their local practice. Investigator will also be advised to follow the general toxicity management guidelines regarding dose interruption and reduction as detailed in Section 5.1.5.

5.2.2.2 Dermatological effects

No specific dermatological exclusion criteria are included in this study, however, patients with any unresolved adverse events from prior therapy greater than CTCAE grade 1 will be excluded from participation. Dermatological treatment should be instituted for patients with any CTCAE grade skin reactions, considered by the investigator to be causally related to DZD9008. Detailed information on the treatment of dermatological adverse events will be included in the "Guidance for the Management of Adverse Events in Studies of DZD9008". Investigators will also be advised to follow the general toxicity management guideline regarding dose interruption and reduction as detailed in Section 5.1.5.

5.2.2.3 Ocular surface effects

Full ophthalmic assessment, including slit lamp examination, will be performed at screening and should be repeated if a patient experiences any visual symptoms (including blurring of vision), with additional tests if clinically indicated. Any clinically significant findings, including those confirmed by the ophthalmologist must be reported as an AE. Photographs may be performed to record any clinically significant findings. Ophthalmology examination results should be collected in the eCRF. Any patient developing corneal ulceration will be permanently discontinued from study treatment and should be followed regularly until resolution of the event.

Patients who wear contact lenses will be advised to discontinue wearing lenses if they have any mild to moderate eye symptoms (CTCAE grade \leq 2) while receiving treatment with DZD9008 until at least one week after symptoms have resolved. If a patient has recurrence of eye symptoms or experiencing any severe (CTCAE grade \geq 3) ocular events they should discontinue wearing their contact lenses until at least one week after treatment with DZD9008 is permanently discontinued. Patients should not use any eye drops or ointment for treatment of eye symptoms has been permanently discontinued. Patient will be advised to consult the investigator promptly if they have any concerns.

Date: July 24,2023

5.2.2.4 Cardiovascular effects

Patients who have unstable cardiac conditions and risk factors for QT prolongations will be excluded from participation in this study. Concomitant use of regular medications that may prolong the QT interval will be restricted whenever feasible (See Appendix H), but patients may receive any medication that is clinically indicated for the treatment of AEs. Electrolyte and vital sign assessments, including pulse rate and blood pressure, will be monitored regularly throughout the study. Regular digital ECG assessments will be as described in Section 6.3.4. The investigator or designated physician will review each ECG prior to discharge from the clinic and may refer to a local cardiologist if appropriate for immediate management of the patient. A paper copy should be filed in the patient's medical records. All digital ECG data will be analyzed. If an abnormal ECG finding at screening or baseline is considered to be clinically significant by the investigator, it should be reported as a concurrent condition.

5.2.2.5 Respiratory effects

Patients with a past medical history of interstitial lung disease, drug-induced interstitial lung disease, radiation pneumonitis which required steroid treatment, or any evidence of clinically active interstitial lung disease will be excluded from participation in this study.

If new or worsening pulmonary symptoms (e.g., dyspnea) or radiological abnormality suggestive of interstitial lung disease, an interruption in study treatment dosing is recommended, and the Sponsor study team should be informed. A questionnaire regarding the results of the full diagnostic workup (including high-resolution computed tomography (HRCT), blood and sputum culture, hematological parameters, bronchoscopy with biopsy as needed) will be sent to investigators. It is strongly recommended to perform a full diagnostic workup, to exclude alternative causes such as lymphangitic carcinomatosis, infection, allergy, cardiogenic edema, or pulmonary hemorrhage. In the presence of confirmatory HRCT scans where other causes of respiratory symptoms have been excluded, a diagnosis of interstitial lung disease should be considered, and study treatment permanently discontinued. In the absence of a diagnosis of interstitial lung disease, study treatment may be restarted following consultation with Sponsor Study Physician.

5.2.2.6 Liver effects

Patients with any evidence of severe or uncontrolled systemic liver disease, including those with known hepatitis B, hepatitis C, human immunodeficiency virus (HIV) or abnormal liver enzymes (defined as AST or ALT > 2.5 x upper limit of normal (ULN), total bilirubin >1.5 x ULN if no evidence of liver metastases; AST or ALT > 5 x ULN, total bilirubin > 3 x ULN in the presence of liver metastases) at screening are excluded from participating in the study. During the study, liver function tests will be monitored regularly during the study and recorded at discontinuation. Patients' laboratory results will be assessed against the FDA's Draft Guidance for Drug Induced Liver Injury (FDA Guidance 2005) with the process described in detail in Appendix G.

5.2.2.7 Hematopoietic effects

Patients with inadequate bone marrow reserve as demonstrated by any of the following laboratory values (absolute neutrophil count $< 1.5 \times 10^9/L$; platelet count $< 100 \times 10^9/L$; hemoglobin < 90 g/L)

Date: July 24,2023

will be excluded from the study. Hematological parameters will be monitored prior to administration of the first dose, weekly during the first cycle of multiple dosing, at the start of each subsequent cycle, and at discontinuation.

5.2.2.8 Renal effect

Patients with abnormal renal function as defined by creatinine > 1.5 x upper limit of normal (ULN) concurrent with creatinine clearance < 50 mL/min at screening are excluded from participating in the study. During the study, kidney function tests (creatinine and urea nitrogen) will be monitored regularly during the study and recorded at discontinuation. In addition, creatine kinase will be routinely monitored throughout the study.

5.2.2.9 CYP450 induction/inhibition

All patients must try to avoid concomitant use of medications, herbal supplements and/or ingestions of foods with known potent inducer or inhibitors on CYP3A4 activity whenever feasible. Such drugs must have been discontinued for a period of 1 week (CYP3A3 inhibitors) or 2 weeks (CYP3A4 inducers) prior to first administration of DZD9008. Patients taking concomitant medications whose disposition is dependent upon intestinal CYP3A4 and/as or transporter proteins and which have a narrow therapeutic index should be closely monitored for signs of changed tolerability as a result increased exposure of the concomitant medication whilst receiving DZD9008. Guidance on medications to avoid, medications that require close monitoring and on washout periods is given in Appendix H. If medically feasible, patients taking regular medication, with the exception of potent inhibitors or inducers of CYP3A4, should be maintained on them throughout the study period. Patients may receive any medication that is clinically indicated for treatment of adverse events.

5.2.2.10 Hemorrhage

DZD9008 was reported to be a potent BTK inhibitor (Investigator's Brochure). Bleeding events, some fatal, including central nervous system, respiratory, and gastrointestinal hemorrhage, have been reported in patients treated with other BTK inhibitors in clinic. Patients receiving antiplatelet or anticoagulant therapies may be at increased risk of hemorrhage. As a precaution, it is suggested per protocol that DZD9008 be withheld for at least 3 days pre- and post-surgery. Patients require anticoagulation or anti-platelet therapy while receiving DZD9008 should be monitored for any signs of bleeding. Patients with hemorrhage should be managed per institutional guidelines or as clinically indicated.

5.2.3 Safety data of DZD9008 in ongoing phase I/II clinical studies

The safety data in the three studies in NSCLC patients (DZ2019E0001, DZ2019E0002 and DZ2020E0001) showed DZD9008 was well tolerated at up to 400 mg once daily, with the majority of adverse events being mild to moderate EGFR-related adverse events (i.e., diarrhea, skin rash, paronychia).

5.2.4 Overall benefit/risk and ethical assessment

For advanced stage NSCLC patients with EGFR or HER2 Exon20ins, there is no effective treatment, and thus prognosis is poor. DZD9008 is a potent, selective and irreversible EGFR TKI which is designed to treat this population of patients with high unmet medical need.

This study is a first-time in-patient study to evaluate DZD9008 in advanced NSCLC with EGFR or HER2 mutation, preferentially focusing on patients with EGFR Exon20ins or HER2 Exon20ins. The starting dose and steps for dose escalation of DZD9008 are defined based on non-clinical toxicity studies. The selected starting dose is predicted to hit the target, in accordance with the ICH S9 Nonclinical Evaluation for Anticancer Pharmaceuticals Section III.A principle of selecting a dose 'that is expected to have pharmacologic effects' (ICH S9). In addition, patients will continue the treatment as long as they are deriving benefit from the treatment according to ICH S9 that 'In Phase I clinical trials, treatment can continue according to the patient's response' (ICH S9). Moreover, predicted human half-life of DZD9008 is ~50 hours, which could potentially achieve continuous inhibition of mutant EGFR pathway and derive clinical activity by once daily dosing. The non-clinical safety profile has not identified any risks that would preclude investigation of DZD9008 in this setting. The study design aims to minimize potential risks, and monitoring is in place for those risks deemed to be most likely or serious.

The selected dose of 200 mg or 300 mg once daily is considered to be appropriate doses with good risk-benefit balance for phase 2. At these two dose levels, by April 3, 2023, the reported incidence of grade 3 and above TEAEs, TEAEs leading to dose interruption and reduction were lower than that of mobocertinib (TAK-788) and other EGFR inhibitors, e.g. afatinib or dacomitinib (19-21); the confirmed ORRs of 200 mg and of 300 mg dose cohort, respectively) in platinum pretreated patients were superior or comparable to that reported in mobocertinib (TAK-788) (21) and amivantamab (JNJ-61186372) (22) studies. Noteworthily, in patients relapsed from or not responded to amivantamab (JNJ-61186372), DZD9008 also showed tumor response.

The investigation of DZD9008 in this patient population appears acceptable, based upon the emerging safety, PK and anti-tumor efficacy of clinical studies, non-clinical safety profile, the lack of effective alternative treatments available to patients, the limited life expectancy due to malignant disease, and the strength of the specific hypothesis under evaluation. Thus, the benefit/risk assessment for this first-into-human Phase 1 study support the oral administration of DZD9008 to patients with advanced EGFR or HER2 mutant NSCLC. The data generated from phase 1 studies support the evaluation of DZD9008 in phase 2 study, focusing on previously treated EGFR Exon20ins mutant NSCLC, according to the proposed study design.

5.3 Discontinuation of investigational product and withdrawal from the study

Patients may withdraw from the study at any time, without prejudice to further treatment and independent of any decision concerning participation in other aspects of the main study. Procedures for withdrawal from the exploratory research are outlined in Section 5.3.2.

Patients may be discontinued from investigational product in the following situations:

- Patient decision. The patient is at any time free to withdraw his/her participation in the study, without prejudice
- Adverse events

• Severe non-compliance to this protocol as judged by the investigator and/or Study Team

- Confirmed disease progression as per RECIST 1.1, unless, in the opinion of the investigator, the patient is still deriving clinical benefit. For France and Canada only: fulfil the following criteria: (a) Absence of clinical symptoms and signs of disease progression (including clinically significant worsening of laboratory values); (b) Stable ECOG PS; (c) Absence of rapid progression of disease or of progressive tumor at critical anatomical sites that requires urgent alternative medical intervention; (d) Investigators must inform subjects that this practice is not considered standard in the treatment of cancer.
- Patients incorrectly initiated on investigational product (Section 5.3.1)
- Pregnancy

Patients who withdraw from the study but are evaluable for safety assessment in Part A escalation will not be replaced. Any patient that is not evaluable in Part A escalation will be replaced to ensure a minimum number of evaluable patients. Once study medication is permanently discontinued it cannot be restarted.

In Part A expansion and Part B, any patient who discontinues study treatment for reasons other than disease progression should have RECIST assessment performed as scheduled in Table 13 and Table 14 of the protocol until disease progression is documented or death occurs, or consent is withdrawn. Study procedure related SAEs and anti-cancer treatment must be captured until the patient no longer has RECIST 1.1 tumor assessment (disease progression or permanent withdrawal from the study).

After database lock, there may be some patients remaining on study treatment. For these patients who are continuing to receive the study treatment, Sponsor will collect information during the treatment period and for 28 days after last dose on SAEs, death (including those due to disease progression), discontinuation due to AEs/SAEs and drug accountability.

5.3.1 Procedures for handling patients incorrectly initiated on investigational product

Patients who fail to meet the inclusion/exclusion criteria should not, under any circumstances, be enrolled or receive study medication. There can be no exceptions to this rule.

Where patients who do not meet the inclusion criteria are enrolled in error or incorrectly started on treatment, or where patients subsequently fail to meet the study criteria post initiation, the investigator should inform the Sponsor Study Physician immediately. The decision on when to discontinue the ineligible patient from the study is based on the medical/safety risk for the patient. The Sponsor Study Physician is to ensure all such contacts are appropriately documented.

Any patient who is found to have failed to comply with all of the selection criteria, but has not started treatment, will be removed from the study.

Date: July 24,2023

Any patient started on treatment in error, as he/she subsequently been found to have failed to comply with all the eligibility criteria, will undergo a risk/benefit assessment by the SRC: if the patient is judged to be receiving clinical benefit, the investigators may choose to continue to dose them with DZD9008.

5.3.2 Procedures for withdrawal from study

Patients are at any time free to withdraw from the study (investigational product and assessments), without prejudice to further treatment (withdrawal of consent). Such patients will always be asked about the reason(s) and the presence of any adverse events. If possible, they will be seen by an investigator and undergo the assessments and procedures scheduled for the post study assessment (see Section 6.3.6). Adverse events should be followed up and study drugs should be returned by the patient.

5.3.3 Interim analysis

An interim data analysis will take place when the last evaluable patient in Part A escalation completes the 28-day continuous dosing (DLT phase) with DZD9008 and finishes all the safety evaluation. Data analysis will be performed and a SRC meeting will be held with the decision of RP2D.

To check futility and also inform the dose selection, one interim analysis will be performed in Part B when 39 patients in full analysis set completed at least 2 RECIST assessments in each cohort. If the number of responses is less than or equal to 7 out of 39 patients in the first stage, then the dose cohort will be stopped. A dose cohort passing the first stage is considered as a "competitive" cohort. When both dose cohorts become competitive, the response rate of two cohorts will be compared to identify the more effective dose. The less effective dose may be dropped after the interim analysis.

Dizal may trigger the discussion with regulatory on the optimal RP2D selection upon emerging efficacy and safety data before interim analysis.

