7.2.2 Part B Dose extension cohort

In Part B, subjects will be randomized into one of the two dose cohorts. Each dose cohort uses a Simon two-stage design.

Considering there are two dose cohorts in the pivotal study and the primary endpoint will be analyzed within each cohort independently, Bonferroni method is employed to control the family-wise type I error (at one-sided 0.025). The analysis in two cohorts will be performed independently, at one-sided significance level of 0.0125.

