7.9.7.1 Tumor response

The analysis population will be the evaluable for response analysis set for Part A and FAS for Part B.

Summaries of the number of patients with best overall response in each part will be provided in the following categories: Complete Response (CR), Partial Response (PR), Stable Disease (SD), Progressive Disease (PD) and Non-Evaluable (NE). Objective response rate and disease control rate will be summarized.

For Part B, p value for the test against the null hypothesis of ORR \le 17\% will reported based on the Simon's two-stage method. ORR and two-sided 97.5\% CI will be calculated based on Jung's method (26) to adjust the bias caused by optional sampling in the Simon's two-stage design and provide the uniformly minimum variance unbiased estimator.

Date: July 24,2023

Data will be analyzed by subgroup (e.g. taken into consideration of the prior treatment) in Part B.

7.9.7.2 **Duration of response**

The analysis population for duration of response will be the subset of the evaluable for response population (Part A) or FAS (Part B) with a best overall response of confirmed CR/PR. Duration of response will be summarized and the number (%) of responding patients with a duration of response > 3, > 6, > 9 and > 12 months will be presented. Or if data are appropriate, response ongoing rates at 6, 9 and 12 months will be estimated based on Kaplan-Meier method. A Kaplan Meier plot and median duration of response (calculated from the Kaplan-Meier) will be presented.

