2.4 Determination of Sample Size

In Part B, patients will be randomized into one of the two dose arms. Each dose arm uses a Simon two-stage design.

Bonferroni method is employed to control the family-wise type I error. The analysis in two arms will be performed independently, at one-sided significance level of 0.0125.

The primary endpoint will be ORR by IRC. Under a Simon two-stage design, a sample size of 103 within each arm is required to test a null hypothesis of ORR at one-sided significance level of 0.0125, with expected ORR of 0.3 and the null hypothesis refers to real world data of 2nd line chemotherapy for NSCLC patients with EGFR Exon20ins [2-3].

In the first stage, patients will be enrolled in each arm. If the number of responses is less than or equal to out of patients in the first stage then the arm will be stopped. If the arm proceeds to the second stage, additional patients will be enrolled to reach a total of 103 patients. If or more responses are observed, then the null hypothesis is rejected in this arm.

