6. INTERIM ANALYSES

To check futility and also inform the dose selection, one interim analysis will be performed when patients completed at least 2 RECIST assessments in each arm.

If the number of responses is less than or equal to \blacksquare out of \blacksquare patients in the first stage, then the arm will be stopped. A dose arm passing the first stage is considered as a "competitive" arm. When both dose arms become competitive, the response rate of two arms will be compared using stage 1 data to identify the more effective arm. $Pr(P_A \ge P_B| \text{ observation})$, defined as probability of true ORR in arm A higher or equal to arm B given the observation at stage 1 assuming a beta (1,1) prior distribution for both cohorts, is used to determine the

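### The stage-1 futility denominator is not defined: read literally, it leaves out early progressions and deaths, and a dose with ORR 17% then passes more often than the 7/39 boundary was set to allow

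*Protocol*

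**What the plan says.** Each Part B cohort uses a Simon two-stage design. Protocol 5.3.3 places the interim look "when 39 patients in full analysis set completed at least 2 RECIST assessments in each cohort". The next sentence gives the boundary: "If the number of responses is less than or equal to 7 out of 39 patients in the first stage", the cohort stops. SAP 6 repeats the condition, "patients completed at least 2 RECIST assessments in each arm", with its stage-1 numbers blacked out. If both cohorts pass, their stage-1 response rates are compared to choose the dose.

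Other parts of the plan bear on who belongs in the 39:

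- **Scan schedule (SAP 2.2).** Scans fall at about week 6 and every 6 weeks after that, until objective progression.
- **Analysis set (protocol Table 10, SAP 3.4).** The FAS needs one dose and IRC-measurable disease at baseline. No follow-up scan is required.
- **Primary ORR (SAP 4.2.1 and Table 1).** A response must be confirmed at a second visit at least 28 days later. A death before the first scan is scored NE and so stays in the denominator.
- **Stage 1 (SAP 2.4).** Stage 1 is described by patients enrolled, with no mention of completed scans.

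**The concern.** The number 39 appears twice in protocol 5.3.3: as the count of patients with two assessments, and as the denominator of the boundary. Someone running the look from that text could reasonably take these to be the same patients. A patient with progression at the first follow-up scan has no further scheduled scan, and a patient who dies or leaves before week 12 has none either. On that reading they never enter the 39.

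On the confirmed-response definition, everyone left out this way is a non-responder. The response rate among those counted is therefore higher than the rate in all treated patients, which is the rate the 7/39 boundary tests. An inactive dose would be stopped less often, the two doses would be compared on a selected group, and the interim and final ORR would have different denominators.

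**Working it through.** **Inputs**

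- Stage 1: 39 patients, pass with 8 or more responses (protocol 5.3.3).
- Null ORR 0.17 (protocol 7.9.7.1); alternative, "with expected ORR of 0.3" (SAP 2.4).
- One-sided level 0.0125 per cohort (protocol 7.2.2); total 103 per cohort (SAP 2.4).
- Median PFS on existing therapy 3.7 months, range 2.6 to 5.9 (protocol 3.2.2). Used only to illustrate a loss rate.

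**The plan's own design**

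P(X ≥ 8), X ~ Bin(39, p), is 0.341 at p = 0.17 (stop chance 0.659) and 0.934 at p = 0.30.

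The final cut-off is blacked out, so I searched for it. With 64 patients in stage 2, 27 of 103 is the smallest cut-off that meets 0.0125: type I error is 0.0111 at 27 and 0.0196 at 26. Power at 27 is 0.801. The stated design is coherent when stage 1 is 39 treated patients.

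**Effect of leaving patients out**

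If a share d is left out and all of them are non-responders, the rate among those counted is 0.17/(1 − d), and P(pass) = P(Bin(39, 0.17/(1 − d)) ≥ 8).

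| d | Rate among counted | P(pass) | Ratio to design | P(stop) |
|---|---|---|---|---|
| 0 | 0.170 | 0.341 | 1.00 | 0.659 |
| 5% | 0.179 | 0.397 | 1.17 | 0.603 |
| 10% | 0.189 | 0.461 | 1.35 | 0.539 |
| 15% | 0.200 | 0.532 | 1.56 | 0.468 |
| 20% | 0.213 | 0.607 | 1.78 | 0.393 |
| 23% | 0.221 | 0.655 | 1.92 | 0.345 |
| 25% | 0.227 | 0.686 | 2.01 | 0.314 |

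**What d might be**

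The documents give no value. Assume exponential PFS and a first scan at 6 weeks (6/4.348 = 1.38 months), so d = 1 − exp(−ln 2 × 1.38 / median):

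- Median 5.9 months: d = 15%, P(pass) 0.531.
- Median 3.7 months: d = 23%, P(pass) 0.651.
- Median 2.6 months, the low end of the cited range: d = 31%, P(pass) 0.776.

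**Expected sample size at ORR 17%**

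By design it is 39 + 64 × 0.341 = 61. At d = 20%, about 39/0.80 = 48.75 patients must be treated to obtain 39 with two scans, so it is 48.75 + 54.25 × 0.607 = 82.

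**Final test**

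With 27 of 103 applied to all FAS patients, type I error goes from 0.0111 to 0.0119 at d = 15% and 0.0121 at d = 23%. It cannot go higher than that to four decimals: with no futility look at all, P(Bin(103, 0.17) ≥ 27) = 0.0121.

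**The case against.** The best reply is that the two-assessment clause is a data-maturity trigger and excludes nobody. Protocol 5.4 uses a similar phrase about two follow-up assessments to time the primary cut-off for all patients. Protocol 5.3.3 names the FAS, which needs no follow-up scan, and SAP 2.4 describes stage 1 by enrolment. The one analysis set that does require a follow-up RECIST assessment is limited to Part A. This stands as a possible reading, so the exclusion is not an explicit rule. It does not close the gap: when the 39th patient completes two scans, more than 39 may have been dosed, and nothing says which 39 count.

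Three further points reduce the size. Protocol 5.3 allows treatment past progression when the investigator sees benefit, and 6.8.1.1 advises going on to the next scan when progression is in doubt, so some week-6 progressors would have a second scan. Protocol 5.3.3 does not say that the two assessments are post-baseline; if the screening scan counts, a week-6 progressor qualifies. And the loss rate is an assumption.

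A reader might infer three stronger conclusions that the documents do not support:

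- **The futility rule loses most of its protection.** At 20% and 23% left out, the stop chance is 0.393 and 0.345 against 0.659, so 60% and 52% of it remains.
- **The pass chance doubles.** That needs about 25% left out, a share the documents do not state.
- **The Simon p-value and the Jung estimate must be recomputed.** Once a cohort has gone on to stage 2, both rest on total responses and the design constants, not on the observed stage-1 split.

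The dose comparison may also matter less now. The SAP lists a dose-dropping memo dated July 27, 2023 and treats the 200 mg test as descriptive. The documents do not show whether the look was run as written.

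**Conclusion.** The concern holds as an undefined denominator with a material effect on one reading. If the 39 are patients with two follow-up scans and 10% to 23% of treated patients are left out, the chance that a dose with ORR 17% passes stage 1 rises from 0.34 to between 0.46 and 0.65. This rests on everyone left out being a non-responder and on an assumed loss rate, of which the 15% to 23% part comes from exponential PFS on existing therapy. That is a fair proxy for a dose no better than existing therapy, but it is not a figure for this trial. The effect is smaller if the baseline scan counts or if patients are scanned beyond progression.

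The harm falls on the futility stop and the stage-1 dose comparison. The final ORR test in the FAS is not compromised. The blacked-out numbers in SAP 6 play no part in this conclusion.

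**What to change.** In protocol 5.3.3 and SAP 6, define stage 1 as the first 39 FAS patients per cohort, in order of first dose. Run the look once each of them has either completed two follow-up assessments (about 13 weeks from first dose, the span SAP Table 2 already uses for two visits) or progressed, died or discontinued earlier. Count anyone without a response as a non-responder, as the primary ORR does. Fixing the 39 by dosing order matters: taking the first 39 to reach any of these endpoints would over-represent early failures.

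If the look has already been done, state which 39 were counted in each cohort, and report the stage-1 count and the dose comparison on this basis.

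The cost is one sentence in each document and no added patients. It restores the design pass chance of 0.34 at ORR 17% and 0.93 at ORR 30%, and gives the interim and final ORR the same denominator rule.
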